Individuals with higher glucose/ HbA1c concentrations at the time of enrolment will be carefully reviewed. Where possible any major changes to insulin regimen thought to be necessary at this time or during study follow-up (e.g. switch from multiple daily injections to pump therapy) will be discussed and implemented in the Run-in Period. BP control will also be reviewed in detail for each participant and any additional assessments necessary scheduled (e.g. 24 hour ambulatory BP monitoring). If these confirm that new therapy is indicated according to the above criteria, this will be discussed and explained. Where there is agreement, such therapy will be initiated (with any additional monitoring required) during the Run-in Period. Cardiovascular risk factors and cholesterol levels will be reviewed with the aim of identifying participants for whom statin therapy may be indicated at present (or in the near future). As in clinical practice, a final decision will be reached in discussion with individual participants.

It is recognised that during the years followed up in the trial many participants will require further changes to be made in their regimens in order to achieve glucose (and other) targets: such changes will be encouraged, supported and implemented.

During the third month of the Run-in Period, participants will be asked to take one tablet of run-in medication (i.e. placebo matching metformin 500 mg) once daily with their evening meal.

e) Baseline assessments: see Schedule of Assessments (page 10). At the beginning of the Run-in Period, relevant items from past medical history, concomitant medications (including duration, type and dose of any previous statin therapy) will be extracted from routine health records and validated with the participant. HbA1c, liver function tests, albuminuria and renal function results will also be captured into the electronic Case Report Form from the recent clinic visit. Where liver function tests and FBC were not performed in routine care within the previous 90 days, or where there are missing data, these will be requested from local laboratories as additional tests.

Height, body weight, ethnicity, and smoking status will be extracted where possible from routine clinic data and validated with patient. The Investigator/ study nurse will be

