15. STATISTICAL ANALYSIS

[name] and Prof [name] will draft the Statistical Analysis Plan (with the study statistician). Primary analysis will be done at the Robertson Centre/ University of Glasgow CTU with University of Dundee receiving copy of stable dataset on study database lock. University of Dundee will maintain a copy of the endpoint and safety datasets and will write data analysis code that mirrors the CTU analyses as validation.

[name], Director of the Robertson Centre for Biostatistics (RCB) at the University of Glasgow, a co-investigator on the study, has calculated that we need to recruit 500 participants (see Section 6; statistical considerations, page 18). Data management, statistical analysis and other aspects of clinical trial support will be supervised by [name].

The data for the CCA cIMT (cIMT) will be analysed using repeated measures regression analysis using all data available for each subject. The hypothesis is that all participants have individual regression lines defining their own disease progression over time and that, on average, the slopes of these regression lines will be reduced by metformin (Glucophage 500 mg bd) treatment. The analysis will be adjusted for cardiovascular risk factors which are strong predictors of IMT progression over and above the baseline measurement to minimise the residual standard deviation and thereby maximise the power of the study. Regression model effect estimates with 95% confidence intervals and associated p-values will be calculated to compare patterns of CCA cIMT progression (primary end-point).

The primary analysis will be extended to determine if the metabolic effects of metformin could potentially explain differential effects on progression of cIMT.

We will report baseline characteristics by treatment group to determine whether randomization was successfully achieved. We will tabulate SARs and SUSARS and the adverse reactions, including hypoglycaemic episodes listed above. The effect of

metformin on the primary endpoint and secondary endpoints will be evaluated using standard mixed linear and survival analysis methods.

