2.4. STUDY OUTCOMES

2.4.1. PRIMARY OUTCOME

The primary outcome will be the rate of progression of average mean far wall cIMT of the common carotid artery over the course of the study (36 months). In the mITT analysis set, as a whole and by treatment group, summary statistics for cIMT and change from baseline will be provided at baseline, 12, 24 and 36 months. The treatment effect estimate, 95% confidence interval (CI) and p-value will be estimated from a repeated measures regression model, with random intercept and random slopes, with cIMT as the outcome, and predictor variables of treatment, baseline cIMT and time. Time will be measured in years from baseline. A time by treatment interaction term will be included in the model, allowing different slopes for the two treatment groups. Adjustments for baseline covariates age, sex, smoking status, systolic blood pressure, BMI, HbA1c and LDL cholesterol will also be included as fixed effects.

A sensitivity analysis will also be carried out extending the model noted above to further adjust for the ultrasound probe frequency used.

Initial analyses will only include the measurements recorded with values < 1.5mm, in line with the Mannheim consensus, but the analyses will be duplicated to include all measurements regardless of value as a sensitivity analysis (see section 2.4.3).

Average mean far wall cIMT of the common carotid artery will be calculated as the average of the left and right mean measurements at each time point, using the following hierarchy:

1. Use all available data for the mean far wall IMT regardless of data availability at other time points.
2. In instances where any duplicate angles are included (resulting in more than six angles per time point), average these duplicate angles first to result in one single measurement per angle.
3. Average next the angles within each side to result in one single measurement for each of the left and right sides
4. Average the remaining left and right measurements to obtain one result per time point

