All continuous secondary and tertiary outcomes will be summarised, overall and by treatment group at each time point; change from baseline will also be summarised. Non-Normally distributed variables will be transformed first. Repeated measures models will be applied to all continuous secondary and tertiary outcomes (except for the tertiary outcome “Progression of averaged maximal distal common carotid artery IMT” which will be analysed as per the primary outcome, using the maximal far wall IMT measurements as the main analysis, calculated as detailed below), assuming a general residual covariance structure, with the change from baseline as the outcome, and predictor variables of treatment, visit number (included as a class variable) and the outcome baseline level where available. The main analyses will test the significance of and provide an estimate of the main effect of treatment in this model. The treatment effect estimate, corresponding 95% confidence interval and p-value will be reported.

As an exploratory analysis to investigate whether the treatment effect varies over time, a visit by treatment interaction term will be added to each model and tested for significance. The p-value for the interaction term will be reported. In addition, the treatment effect, 95% confidence interval and p-value will be reported for each visit.

The main analysis of the averaged maximal distal IMT of the common carotid artery will use solely the maximum far wall cIMT measurements, and unlike the main analysis of the primary outcome, will not restrict to values < 1.5mm. A sensitivity analysis will also be performed using both the maximum near wall and the maximum far wall measurements as detailed in section 2.4.3.

The calculation of the averaged maximal distal IMT at each time point will use the following hierarchy:

1. Use all available data for the maximum far wall IMT regardless of data availability at other time points.

2. In instances where any duplicate angles are included (resulting in more than six angles per time point), average these duplicate angles first to result in one single measurement per angle.
3. Average next the angles within each side to result in one single measurement for each of the left and right sides
4. Average the remaining left and right measurements to obtain one result per time point

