The frequency of hypoglycaemia will be analysed using a Negative-Binomial regression model, accounting for over-dispersion using the scale option, with the logarithm of time as an offset variable. The frequency of the minor hypoglycaemia will be further adjusted for the method of collection, with results provided for all collection methods combined. Each method of collection will then be analysed and reported separately. In instances where there has been a change in the method of collection, the method that was most commonly used for each subject will be adjusted for.

New onset microalbuminuria will be analysed in a time to event analysis using a Cox Proportional Hazards Model. The results will be summarised graphically using the Kaplan-Meier method. Similar methods will be used to analyse the first occurrence of biochemical vitamin B12 deficiency.

For the retinopathy outcome, logistic regression analysis will be performed. If the numbers of patients with retinopathy are too small to allow logistic regression analysis to be performed, Fisher's exact test will be used instead.

The regression model for the primary outcome will be extended to determine if glucose-and/or lipid-lowering effects of metformin could potentially explain differential effects on the progression of cIMT. This will be accomplished by including baseline and on-treatment HbA1c and LDL-cholesterol values as time-dependent covariates in the model described above for the primary outcome.

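### SAP 2.4.2 names no baseline covariates for the Cox models of new-onset microalbuminuria and vitamin B12 deficiency; read as unadjusted, both tests are valid but less powerful than the collected data allow

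*SAP*

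**What the plan says.** For albuminuria, SAP 2.4.2 states: "New onset microalbuminuria will be analysed in a time to event analysis using a Cox Proportional Hazards Model". For the tertiary B12 outcome (a value below 150 pmol/L) it adds: "Similar methods will be used to analyse the first occurrence of biochemical vitamin B12 deficiency". Kaplan-Meier curves accompany the models. No model terms are listed for either. Protocol section 15 is no more specific: the "primary endpoint and secondary endpoints will be evaluated using standard mixed linear and survival analysis methods".

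Elsewhere the SAP does write out its adjustments:

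- Primary model (SAP 2.4.1): baseline cIMT, and "Adjustments for baseline covariates age, sex, smoking status, systolic blood pressure, BMI, HbA1c and LDL cholesterol will also be included as fixed effects".
- Continuous secondary and tertiary outcomes (SAP 2.4.2): "predictor variables of treatment, visit number (included as a class variable) and the outcome baseline level where available".
- Minor hypoglycaemia (SAP 2.4.2): "The frequency of the minor hypoglycaemia will be further adjusted for the method of collection".

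Protocol section 15 explains the adjustment of the cIMT analysis by the use of "strong predictors of IMT progression over and above the baseline measurement to minimise the residual standard deviation and thereby maximise the power" of the study. That reason is given for cIMT only.

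The baseline data are collected. The Schedule of Assessments has vitamin B12, HbA1c, blood pressure and U&E at both R1 and Visit 1. Protocol 7.3(e) says that "HbA1c, liver function tests, albuminuria and renal function results will also be captured into the electronic Case Report Form". Protocol 6(b), however, describes the recorded microalbuminuria item as a positive or negative status.

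**The concern.** An SAP that lists covariates for its other models and none for these two is naturally read as planning unadjusted Cox models. Leaving out a prognostic baseline variable does not invalidate a randomised comparison, but it costs power and moves the hazard ratio closer to 1 than the hazard ratio conditional on that variable.

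The stakes are modest but real. Albuminuria is one of the secondary outcomes counted when the SAP asks whether at least two have improved significantly, and Protocol 6(d) concedes lower power for endpoints other than the continuous ones. B12 deficiency is a recognised metformin risk. The stricter safety threshold of 110 pmol/L in SAP 2.4.5.4 is reported without testing, so the Cox model is the formal test of deficiency.

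**Working it through.** **Nearest stated figure.** Neither outcome has a stated event rate, hazard ratio (HR) or power. The closest figure is for retinopathy in Protocol 6(d): 400 participants, 13.7% three-year rate, HR 0.40, 80% power.

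- Metformin rate: 1 − (1 − 0.137)^0.40 = 5.72%.
- Expected events, 200 per arm: 200 × (0.137 + 0.0572) = 38.8.
- Schoenfeld power: Φ(√(38.8/4) × |ln 0.40| − 1.96) = Φ(0.895) = 81.5%.

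The stated 80% is reproduced.

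**Simulation of the two models.** The rates, effects and predictor strengths are assumptions. The hazard is λ·exp(θ·treatment + β·z), with z a standard-normal baseline covariate and λ set to give the chosen three-year control rate. There are 400 participants at risk, allocated 1:1, with three years of annual detection, Efron handling of ties, a Wald test at 1.96 and 1000 runs per setting. Each data set is fitted without and with z.

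Microalbuminuria, conditional HR 0.50, power without → with adjustment:

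| Control rate | HR 1.5 per SD | HR 2 per SD | HR 3 per SD | Events |
|---|---|---|---|---|
| 10% | 42% → 43% | 40% → 42% | 40% → 45% | 30–31 |
| 20% | 73% → 74% | 75% → 76% | 67% → 77% | 61–63 |
| 30% | 90% → 91% | 86% → 91% | 83% → 94% | 93–97 |

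The gain is about 1–5 points at HR 1.5–2 per SD and 5–11 at HR 3. Differences of 1–2 points are within simulation error. The unadjusted median HR is 0.51–0.55, against about 0.50 adjusted.

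A smaller risk set tells the same story. It has 340 participants, about 80% of the 379 + 50 = 429 in Protocol Appendix 6, a control hazard of 5–10% a year and a score SD of 0.5–1.2 on the log-hazard scale. Power goes from 48% to 50% (weak score), 70% to 75% (moderate) and 58% to 69% (strong).

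B12 deficiency, conditional HR 2.0:

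| Control rate | HR 2 per SD | HR 3 per SD | HR 5 per SD | Events |
|---|---|---|---|---|
| 5% | 42% → 44% | 37% → 42% | 30% → 37% | 27–29 |
| 10% | 69% → 72% | 63% → 71% | 47% → 65% | 53–57 |

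The gain is about 2–18 points. At the 10% rate the unadjusted median HR is 1.96, 1.87 and 1.71.

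With no prognostic covariate, adjustment changes nothing. Under the null (20% rate, covariate HR 3 per SD), rejection is 4.1% unadjusted and 4.8% adjusted, so size is not inflated.

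**B12 simulated as a concentration.** Assumptions: 400 participants, mean 330–420 and SD 110–150 pmol/L, within-person SD of change 60–90, cases already deficient at baseline removed.

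- For falls of 40–50 pmol/L, adjusting for log baseline B12 adds 5–8 points (for example 69% to 77%, and 52% to 59%).
- Those runs had unequal null rejection, 3.4% unadjusted and 5.3% adjusted. The critical values for these sizes are 2.120 and 1.935, a difference of 0.185. Size alone would therefore move 69% to Φ(0.496 + 0.185) = 75% and 52% to Φ(0.050 + 0.185) = 59%. These gains cannot be taken at face value.
- Repeated with Efron ties, where both models stayed at or below 5%, the gain is about 9–10 points for falls of 25–50 pmol/L. It is not a size artefact.
- At the 80 pmol/L fall cited in Protocol 6(b), power is about 98% or higher either way.

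**The case against.** **The SAP does not say that the models contain treatment only.** A reader might infer this, but SAP 2.4.2 lists no terms at all. What can be shown is an unspecified covariate set; an unadjusted model is the natural reading, not a stated one.

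**A reader might also infer that the hazard ratios would be biased towards 1.** They would not. The unadjusted hazard ratio is a valid marginal estimate under randomisation. Its distance from the conditional one is non-collapsibility, and preferring the conditional value is a choice of estimand.

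**Nothing in the documents shows that the microalbuminuria predictors are strong.** No strength is given for any of them, and eligibility narrows the range of HbA1c and eGFR. This stands, and it limits the microalbuminuria claim to a modest gain.

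**The analogy with the continuous outcomes is imperfect.** A positive or negative baseline status is constant among participants free of microalbuminuria, so it cannot be a covariate. Protocol Appendix 5 says local assay results are recorded, so quantitative values may exist, but it allows ratios, simple concentrations and timed collections, which do not form one variable. This stands for albuminuria. It does not touch B12, HbA1c, systolic blood pressure or eGFR.

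**The consequence is slight.** B12 deficiency is tertiary, albuminuria is one of eight secondary measures, and the B12 gain vanishes at the protocol's own fall. This stands too. It makes the point minor without removing it, since the stated reason for adjusting cIMT applies equally here.

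**Conclusion.** The concern holds as a minor point. No baseline covariate is specified for either Cox model, and if they are run unadjusted the tests are valid but less powerful than the collected data allow.

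B12 is the clearest case, because baseline B12 is an earlier value of the variable that defines the event. The gain is roughly 2–18 points for assumed predictor strengths of HR 2–5 per SD, and almost nothing if the fall is 80 pmol/L. For microalbuminuria it is about 1–5 points with moderate predictors, and reaches 5–11 only at HR 3 per SD, for which the documents offer no support. The direction is secure; every size rests on assumed rates, effects and predictor strengths.

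**What to change.** Before unblinding, add to SAP 2.4.2:

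- **B12 deficiency:** Cox model with treatment and log baseline B12.
- **New-onset microalbuminuria:** Cox model with treatment, baseline HbA1c, systolic blood pressure and eGFR. Add quantitative baseline albumin only if it is held in a common unit.
- **Missing baseline values:** apply the multiple-imputation rule of SAP 2.4.1. It now covers only primary-model covariates, so extend it to baseline B12 and eGFR; otherwise participants would drop out of these models.
- **Reporting:** adjusted hazard ratio as the main result, unadjusted hazard ratio as a sensitivity analysis, Kaplan-Meier curves unadjusted.

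The cost is SAP wording and a small extension of the imputation code; the core covariates need no new data. There are two downsides. The main hazard ratio becomes conditional on the covariates and should be labelled so. The number of terms must also suit the events: with about 30 microalbuminuria events, four terms leave 30/4 = 7.5 events per term and a fifth leaves 6, whereas about 61 events leave 61/4 ≈ 15. The two-term B12 model has about 27/2 ≈ 14 even at the lower assumed rate. If blinded pooled counts are low, shorten the microalbuminuria list before unblinding.

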2.4.3. IMPUTATION/SENSITIVITY ANALYSIS

The following sensitivity analyses involving imputation of missing data will be carried out:

- A multiple imputation will be used to analyse the primary outcome, with imputation of cIMT measurements that are missing other than because the patient had died, withdrawn consent or was censored due to end of follow-up. The multiple imputation approach will use the baseline covariates included in the adjusted primary outcome model (age, sex, smoking status, systolic blood pressure, BMI, HbA1c and LDL cholesterol) after imputation of any missing values.
- A similar approach will be used to impute missing retinopathy and endothelial function data.

The following sensitivity analyses will also be included:

- Inclusion of all mean far wall cIMT measurements of the common carotid artery for the calculation of the averaged mean for the primary outcome, regardless of whether the individual measurements are < 1.5mm or not, using the same hierarchy as detailed above in section 2.4.1.
- Inclusion of both the maximum near wall and the maximum far wall IMT measurements in the calculation of the averaged maximal distal IMT of the common carotid artery at 12, 24 and 36 months for the tertiary outcome.

The calculation of the averaged maximal distal IMT at each time point for the sensitivity analysis will use the following hierarchy:

1. Use all available data for the maximum near wall and the maximum far wall IMT regardless of data availability at other time points.
2. Take the single absolute maximum value across both the near wall and the far wall for all available angles and sides, resulting in one maximum value at each time point.

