Other assessments: Serum C-peptide will be measured in local laboratories at the screening visit: participants will be withdrawn before randomisation in cases where this is > 200 pmol/L (= 0.2 nmol/L or 0.6 ng/ml). Although the risk of lactic acidosis is almost negligible,⁴⁸ plasma lactate will be monitored according to the Schedule of Assessment in local laboratories; participants with values > 3.0 mmol/L (>27 mg/dL) will be recalled for clinical assessment within one week and treatment discontinued if this level is sustained: where possible, blood samples for lactate will be performed without a tourniquet ("uncuffed") and following minimal exertion (this approach will be adopted for all repeat lactate measurements). Full blood count and serum vitamin B12 (cobalamin) concentrations will also be monitored during the study in view of the small risk of metformin induced B12 deficiency identified in recent papers by the applicants (CS/ SL): concentrations fell by 80 pmol/L with prolonged therapy, although rarely outwith the reference range (150-550 pmol/L).^{18,49} Any individuals whose levels do fall below the reference range (<150 pmol/L) and who do not wish to discontinue therapy will be referred to their primary care physician for consideration of replacement therapy.

Long-term follow-up: The primary and secondary outcomes of the study are robust, but they are surrogates for long-term CVD risk. Where national competent authorities permit, we will seek informed consent from all participants to "flag" them in national systems using national health numbers to permit outcome assessment and to receive notifications of deaths. This will be led by applicant IF who has particular expertise in this area.

c) Sample handling storage and shipping

Following pre-processing and aliquoting, blood and urine samples will be stored locally at -70°C or -80°C according to the study Sample Handling Plan prior to shipping to the central laboratory in Glasgow (Applicant NS). All study samples will be sent on dry ice using contracted couriers at annual intervals. All samples will be stored on arrival at -80°C .

d) Statistical considerations/ number of subjects to be included in the study

Primary endpoint cIMT: For the primary endpoint of cIMT there will be a baseline measurement and repeat measurements at year 1, 2 and 3 (visits 8, 12 and 16). All those with a baseline and at least one follow up measurement will be included in analysis.

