No imputation of the primary outcome will be performed for the main analysis (the model described above will make use of all analysable data available for a subject). However, if any baseline covariates included as adjustments in the model (systolic blood pressure, BMI, HbA1c and LDL cholesterol) have neither treatment visit 1 data, nor run-in visit 1 data available, multiple imputation will be used, using the other baseline covariates included as adjustments with complete data at baseline (including age, sex and smoking status).

The analysis will be repeated for the PP population.

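### The imputation rule for missing cIMT scans names seven baseline covariates but not randomised arm, baseline cIMT or the participant's other scans, so the sensitivity analysis can mislead if followed literally

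*SAP*

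**What the plan says.** SAP 2.4.1 describes a repeated measures model with random intercept and slopes, "with cIMT as the outcome, and predictor variables of treatment, baseline cIMT and time", plus a time-by-treatment interaction. It lists the covariates in a separate sentence: "Adjustments for baseline covariates age, sex, smoking status, systolic blood pressure, BMI, HbA1c and LDL cholesterol will also be included as fixed effects". On missing scans it says "No imputation of the primary outcome will be performed for the main analysis", because "the model described above will make use of all analysable data available for a subject".

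SAP 2.4.3 adds a sensitivity analysis that imputes cIMT values "missing other than because the patient had died, withdrawn consent or was censored due to end of follow-up". The method is given in one sentence: "The multiple imputation approach will use the baseline covariates included in the adjusted primary outcome model (age, sex, smoking status". The bracket goes on to systolic blood pressure, BMI, HbA1c and LDL cholesterol, and closes. These are the same seven variables that SAP 2.4.1 calls baseline covariates. Treatment and baseline cIMT stand outside that group in SAP 2.4.1, so the reference does not bring them in. No other section adds them, and no imputation method or number of imputations is given.

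The rule then carries over to two secondary outcomes: "A similar approach will be used to impute missing retinopathy and endothelial function data".

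**The concern.** An imputation model should carry at least the terms of the analysis it feeds. Here the quantity of interest is the difference between arms in within-person slope. Two omissions matter, for different reasons.

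- **Arm.** Scans imputed without arm carry no treatment difference of their own, so the estimate is diluted.
- **The participant's own scans, including baseline.** A missing scan is replaced by a draw from people with similar covariates, not from that person's own level. Between-person spread then enters a within-person slope.

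The information is available. Protocol section 6 d) expects a baseline scan and some follow-up for everyone analysed: "All those with a baseline and at least one follow up measurement will be included in analysis". Read literally, the check on missing scans would use less information than the analysis it checks. A real effect could look fragile for reasons unrelated to missing data. If scans are lost unevenly between arms, an effect could also appear where there is none.

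**Working it through.** **Inputs from the documents** (Protocol section 6 d), SAP 1.3 and 1.4): 200 per arm, net of drop-out; difference 0.0167 mm in 3-year progression; SD of progression 0.05 mm; 5% level (taken as two-sided); scans at 0, 12, 24 and 36 months.

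**Assumed, because the documents do not give them:** 2%, 5% or 10% of follow-up scans imputed; between-person cIMT SD 0.10–0.15 mm; R-squared of the seven covariates 0.3; half of the change variance due to measurement error; baseline scan treated as one of the repeated outcomes.

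**Step 1: the plan's own figure.** SE = 0.05 × √(2/200) = 0.0050. Then 0.0167/0.0050 = 3.34, and 3.34 − 1.96 = 1.38, which gives power 91.6%. The stated 90% is reproduced.

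**Step 2: standard error under the literal list, 10% imputed, by hand.** The weights that turn four scans into a 3-year slope are −0.9, −0.3, 0.3 and 0.9. The squares for the three follow-up scans sum to 0.99.

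- Residual between-person variance at SD 0.15: 0.7 × 0.15² = 0.01575.
- Within-imputation variance per person: 0.0025 + 0.1 × 0.99 × 2 × 0.01575 = 0.0056.
- Between-imputation variance per person: 0.1 × 0.99 × 0.01575 = 0.0016.
- Rubin's rules with 10 imputations: 0.0056 + 1.1 × 0.0016 ≈ 0.0073, so SE = √(2 × 0.0073/200) ≈ 0.0086.

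The same steps at SD 0.10 give about 0.0068. Both compare with 0.0050 in Step 1.

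**Step 3: attenuation.** Under the literal list the expected effect is about (1 − imputed fraction) × 0.0167, which is 0.0159 mm at 5% and 0.0150 mm at 10%.

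**Step 4: simulation**, scans missing completely at random, 10 imputations, Rubin's rules. Ranges span SD 0.10–0.15 mm. The main model on the same data has power 91–94%.

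| Imputation model | 2% imputed | 5% | 10% |
|---|---|---|---|
| Seven covariates only: share of effect kept | 0.98 | 0.95–0.96 | 0.90–0.91 |
| Seven covariates only: power | 84–88% | 65–79% | 37–61% |
| Own scans added, arm omitted: share of effect kept | 0.99 | 0.98 | 0.95 |
| Own scans added, arm omitted: power | 91–93% | 91% | 89–90% |
| Arm and all scans added: power | 91–94% | 92–93% | 91% |

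Among simulated trials significant in the main model, the literal version loses significance in 5–10%, 15–27% and 36–59%. With own scans but no arm the figure is 1–4%; with arm and all scans it is at most 2%. Using 50 imputations leaves literal power at 39–62% at 10% imputed, so the number of imputations is not the cause.

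**Step 5: which omission does what.** A separate simulation (SD 0.15, R-squared 0.25, scan-error SD 0.025 mm, 10% imputed) gave:

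| Imputation model | Estimate (mm) | SE | Power |
|---|---|---|---|
| Literal list | 0.0149 | 0.0088 | 36% |
| Arm added, not scans | 0.0166 | 0.0089 | 45% |
| Scans added, not arm | 0.0156 | 0.0050 | 89% |
| Both added | 0.0164 | 0.0050 | 91% |
| Main model, no imputation | 0.0163 | 0.0050 | 91% |

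Omitting arm causes the attenuation; omitting own scans causes nearly all the power loss.

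**Step 6: missingness that depends on arm and baseline.** Suppose there is no true effect, and 10% of all month-36 scans are missing, all from active-arm participants with above-median baseline. That is 20% of the active arm's month-36 scans.

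- The above-median half of a normal distribution lies 0.798 SD above the mean. The covariates leave 0.7 of that unexplained: 0.7 × 0.798 = 0.559 SD.
- The imputation regression is fitted to the remaining 90% of scans, whose mean is lower, so the shortfall becomes 0.559/0.9 = 0.621 SD.
- Spurious benefit: 0.20 × 0.9 × 0.621 × SD = 0.112 × SD, which is 0.011 mm at SD 0.10 and 0.017 mm at SD 0.15.

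Simulation gave the same 0.011–0.017 mm, with 33–50% of null trials rejected. Under completely random loss the literal rule rejected about 1%. A milder form of the pattern gave a bias of 0.005–0.007 mm.

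**The case against.** The strongest reply is that the sentence says what the imputation *will use*, not that it will use nothing else. It names no engine and reads like a summary. In a joint or chained imputation across visits the other scans enter by construction, because they are themselves being imputed. On that reading only arm is missing, and at 10% imputed the estimate keeps about 0.95 of the effect and loses a few points of power. That stands, and it limits the point. It does not remove it: nothing in the SAP says the other scans enter, nothing on either reading brings in arm, and two analysts following the text could obtain materially different results.

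It is also fair that the imputed fraction may be small. Scans missing through death, withdrawn consent or end of follow-up are not imputed, and participants with inadequate images are withdrawn before randomisation (Protocol 7.3 f). At 2% imputed even the literal rule keeps about 84–88% power.

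The simulations assume balanced data. Appendix 6 of the protocol shortens follow-up for 50 participants, so the real data will not be balanced. The figures are indicative.

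Three stronger readings are tempting and are not supported.

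- That the primary result is at risk: the main model imputes no cIMT, and no decision rule is attached to the imputed result.
- That the flaw is harmless because it only pulls toward zero: this holds under completely random loss, but Step 6 shows the opposite direction is possible.
- That a real finding would probably lose significance at 5% imputed: the figure is 15–27%.

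**Conclusion.** The concern holds for this sensitivity analysis. As written, the rule omits arm, baseline cIMT and the participant's other scans. If it is followed literally and scans are missing completely at random, power at the design effect is about 84–88%, 65–79% and 37–61% at 2%, 5% and 10% imputed, against about 90% or more with the omitted terms included. If own scans are used and only arm is left out, the loss is small. If loss of scans depends on arm and baseline cIMT, the literal rule can also produce a spurious benefit, so it is not safe against false positives.

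The direction under random loss is stable. The size depends on the imputed fraction, between-person SD, covariate R-squared and error share, none of which the documents give. In a wider grid (R-squared 0.1–0.5, error share 0.3–0.7) literal power at 10% imputed ranged from 25% to 68%, against 90–94% with arm and all scans. The same gap for retinopathy and endothelial function follows in principle but was not quantified. Retinopathy is graded only at 0 and 36 months, so the figures above do not transfer to it.

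**What to change.** State in SAP 2.4.3 that the cIMT imputation model includes randomised arm (or is run separately by arm), baseline cIMT and all observed cIMT visits, together with the seven covariates. Name the imputation method and the number of imputations in the same place.

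For the two outcomes handled in a similar way, state that imputation includes arm plus baseline grade for retinopathy, and arm plus the other visits for endothelial function, restricted to the centres that measure it.

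The cost is SAP wording and analysis code. Arm and all scans are already collected; no visit, participant or primary analysis changes.
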